# 9.1. Analysis of the Primary Safety Endpoint

Each table number and population will clearly state; results will be presented using the Table 1a design. Results will be tabulated based on the number of patients experiencing one or more device-related or procedure-related serious adverse events at 12 weeks post-procedure.

The statement of the primary research question that will be addressed is as follows:

What percentage of the patients in the ITT population experienced one or more device-related or procedure-related serious adverse events within 12 weeks (84 days) of the index study procedure?

The statement of the secondary research question is specific below:

Is there a difference in the percentage of patients in the ITT population who experienced one or more device-related or procedure-related serious adverse events within 12 weeks (84 days) of the index study procedure based on the generation of the device, voltage, and single vs. double treatment?

The following model will be used to compare the groups identified within each Comparison Set. The dependent variable is the classification of each patient relative to experiencing a device-related or procedure-related serious adverse events at within 12 weeks (84 days) of the index study procedure [variable: DRPRSAE]. Contrast statements will be used to derive the estimates for each pair-wise comparison of a group.

Version 1.0 Confidential Page 32 of 42

```
PROC GLIMMIX DATA=COMP_SET_1;
    CLASS COMP_SET_1_GROUP;
    MODEL DRPRSAE = COMP_SET_1_GROUP / DIST=BINARY LINK=LOGIT SOLUTION;
    RANDOM INTERCEPT / SUBJECT=SUBJID_N;
    LSMEANS TRTAN / DIFF CL;
RUN;
```

Sensitivity analyses will be performed using the FAS and PP populations. Results will be presented in the analysis table 14.4.1 entitled Summary of the Device-Related or Procedure-Related Serious Adverse Events Within 12 weeks (84 days) of the index study procedure (ITT Population) and table 14.4.1.1 entitled Summary of the Device-Related or Procedure-Related Serious Adverse Events Within 12 weeks (84 days) of the index study procedure (FAS Population) and table 14.4.1.2 entitled Summary of the Device-Related or Procedure-Related Serious Adverse Events Within 12 weeks (84 days) of the index study procedure (PP Population). Listing 16.4.11 entitled Adverse Events provides supportive data for Tables 14.4.1, 14.4.1.1, and 14.4.1.2 will be sorted by site number and patient number.

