12.4.3 Primary Endpoint Analysis

The primary endpoint of the study is the proportion of participants experiencing one or more device- or procedure-related serious adverse events within 12 weeks post-procedure. The analysis will be performed using the ITT population, then tabulated and reported for each treatment arm and overall. Fisher's exact test will be used to assess differences which may be present between groups

Additionally, an overall summary of AEs will be provided including the number of events and percent of participants with any AEs, SAEs, and UADEs. For each type of event, the number of events and number and percent of participants with the event will be provided. Separate summaries of all adverse events will be summarized by seriousness and by relationship to device and procedure.

Only events occurring at or after the index procedure will be counted for the purpose of safety analysis. Events occurring prior to the index procedure will be considered as medical history.

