### 3. INTRODUCTION

This statistical analysis plan (SAP) describes the planned statistical methods to be used during the reporting and analysis of data collected under the Clinical Investigation Protocol entitled Safety and Feasibility of Endoscopic Application of a Novel Therapy for Duodenal Mucosal Regeneration in the Treatment of Type II Diabetes (REGENT-1-US Study), Doc. No. 346. This SAP should be read in conjunction with the study protocol and case report forms (CRFs).

The REGENT-1-US study is a multicenter, open-label, treatment-only study conducted in the United States. The study is designed to assess the feasibility and preliminary safety of the Endogenex device for endoscopic duodenal cellular regeneration in patients with type 2 diabetes (T2D) inadequately controlled on glucose-lowering medications. The protocol enrolled patients who were treated with non-insulin glucose-lowering agents; a tabulation of the treatment and number of patients is presented below.

Device Generation 1 / 600	Device Generation 1 / 600	Device Generation 2 / 750	All
Volts / Single Treatment	Volts / Double Treatment	Volts / Double Treatment	Patients
(n)	(n)	(n)	(n)
3	7	10	20

This plan is developed for analysis and reporting of the 48-week follow up data. The SAP may be revised in the future to address additional follow up data analysis beyond 48 weeks, if necessary.

Patients are considered enrolled in the study once the patient has passed endoscopic screening and proceeded to the Index procedure. *Screen failures* are defined as patients who consented to participate in the clinical study and started the screening tests specified by the protocol but are not subsequently enrolled into the study. Procedure success was defined as at least 6cm of duodenum was successfully treated.

The following analysis populations are defined for the presentation of the results from this study: *Intent-to-Treat* (ITT), *Full Analysis Set* (FAS) [referred to in the study protocol as the modified Intent-to-Treat (mITT) population], *Per-Protocol* (PP) and *Completed Cases* (CC). (Ref. Section 11.3 of the study protocol).

The primary and secondary safety analyses will be performed using the ITT population. The primary effectiveness analyses will be performed using the FAS population. The Per-Protocol population and Completed-Cases population will be used for the sensitivity analyses of the primary and secondary effectiveness endpoints.

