### Change = Post- Procedure value - baseline value.

- Missing data may have an impact upon the interpretation of the trial data. However, given the feasibility nature of this study, coupled with the number of patients within a Comparison Set, multiple imputation will not be attempted. The primary presentation of the results will be based on the observed data. A methodology is defined in this section for addressing missing dates.
- Date variables will be formatted as DDMMMYYYY for presentation; SAS Date9. format.
- Months will be converted to days by dividing by 30.42 and rounding up to achieve an integer value.
- SAS® Version 9.4 will be the statistical software package used for all data analyses.
- All data from this study will be presented in a listing.
- Table and listing numbering will follow ICH guidelines for post-text table and listing numbering.

For Adverse Event reporting, which includes primary and secondary variables, the primary analysis will be based on Patient counts (e.g., the number and percentage of Patients with events among the total number of Patients). The data will be presented in the format of p% (x/N) [e], with p and x being the percentage and number of Patients with events, respectively, N being the sample size of the analysis population, and e being the total number of events occurred in the x Patients. Asymptotic confidence limits will be presented based on the normal approximation to the binomial distribution for differences in proportions. Exact confidence intervals will be used for all other presentations.

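### SAP 9.1 replaces the protocol's Fisher's exact test for group differences in the primary safety endpoint, without explanation, with a random-intercept logit whose odds ratios the data cannot determine

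*SAP*

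**What the plan says.** **Protocol.** Section 12.4.3 has the primary endpoint analysed in the ITT population, "tabulated and reported for each treatment arm and overall". It then says that Fisher's "exact test will be used to assess differences which may be present between groups". The arms are 600V and 750V, ten participants each (12.2).

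**SAP groups.** In section 3, "a tabulation of the treatment and number of patients is presented below": 3 patients with Generation 1 / 600V / single treatment, 7 with Generation 1 / 600V / double, and 10 with Generation 2 / 750V / double. Section 7 builds two Comparison Sets from these. Set 1 is 3 v 7 v 10, and Set 2 is 3 v 17. Neither sets the ten 600V patients against the ten 750V patients.

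**SAP model.** Section 9.1 states: "The following model will be used to compare the groups identified within each Comparison Set". The outcome is one classification per patient. The code fits a binary logit with group as the only fixed effect, plus "RANDOM INTERCEPT / SUBJECT=SUBJID_N" and "LSMEANS TRTAN / DIFF CL". The text promises contrast statements for each pair, but the code contains none. The SAP never names Fisher's test and nowhere explains the change. Section 2 records version 1.0 as the initial version.

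**SAP intervals.** Section 7 says: "Asymptotic confidence limits will be presented based on the normal approximation to the binomial distribution for differences in proportions". It continues: "Exact confidence intervals will be used for all other presentations".

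**Status.** Section 7.1 calls testing informative, with no multiplicity adjustment. Section 9 says there are no formal hypothesis tests.

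**The concern.** SAP 9.1 poses a secondary research question on the trial's only primary endpoint: does the percentage of patients with such an event differ by device generation, voltage and single or double treatment? The protocol's method can be computed for any table of counts. The SAP's method has three weaknesses.

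- A patient-level random intercept needs repeated records per patient, and here there is one. Any odds ratio reported, with its Wald limits, would depend on a variance on which the data are silent.
- The logit itself has no finite contrast when a group has no events or all events. With serious events and groups as small as three, that is a likely outcome.
- The companion limits for a difference in proportions can shrink to a point when no events occur. In a first-in-human safety study that would suggest certainty where there is almost no information.

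**Working it through.** The documents give no expected event rate and no computed figure to reproduce. All rates and counts below are assumptions. Group sizes come from the table in SAP 3 (3 + 7 + 10 = 20). Everything was computed in Python; no SAS was run.

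**1. Identification.** Let group g have intercept b_g and let the random intercept have SD s. With one record per patient, the likelihood depends only on the marginal event probability q_g = E[expit(b_g + sZ)], with Z standard normal:

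log L = sum over groups of [e_g ln q_g + (n_g - e_g) ln(1 - q_g)].

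For any s, b_g can be chosen so that q_g = e_g/n_g, so the maximum is the same for every s. With assumed counts 1/3, 1/7 and 2/10:

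- [ln(1/3) + 2 ln(2/3)] + [ln(1/7) + 6 ln(6/7)] + [2 ln 0.2 + 8 ln 0.8] = -1.910 - 2.871 - 5.004, about -9.784.

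| Intercept SD | log L | log OR, group 2 v 1 | OR |
|---|---|---|---|
| 0 | -9.784 | -1.10 | 0.33 |
| 1 | -9.784 | -1.28 | 0.28 |
| 2 | -9.784 | -1.70 | 0.18 |
| 4 | -9.784 | -2.79 | 0.06 |

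Some results do not move with s. The fitted percentages stay at 33.3%, 14.3% and 20.0%, and the sign of each contrast is fixed. With a common rate of 4/20, log L = 4 ln 0.2 + 16 ln 0.8 = -10.008. The likelihood-ratio statistic is therefore 2 x (10.0080 - 9.7844) = 0.447 on 2 df at any SD.

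**2. No finite contrast, even without the random intercept.** A group of size n has 0% or 100% events with probability d(n) = (1 - p)^n + p^n. At p = 10%, d(3) = 0.730, d(7) = 0.478 and d(10) = 0.349, so P(at least one such group in Set 1) = 1 - 0.270 x 0.522 x 0.651 = 0.908. For equal rates across groups:

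| Assumed rate | 5% | 10% | 20% | 30% |
|---|---|---|---|---|
| Set 1, at least one such group | 98% | 91% | 66% | 44% |
| 7 v 10 contrast not finite | 88% | 66% | 29% | 11% |
| Set 2, 3 v 17 not finite | 92% | 78% | 53% | 37% |

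**3. The code.** TRTAN in the LSMEANS statement appears in neither CLASS nor MODEL.

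**4. Limits for a difference.** The uncorrected half-width is 1.96 x sqrt[p1(1-p1)/n1 + p2(1-p2)/n2]. For 0/7 v 0/10 it is zero, giving [0, 0].

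- Exact per-group upper limits for the same data, 1 - 0.025^(1/n), are 41.0% (0/7) and 30.8% (0/10).
- A continuity correction of 0.5 x (1/7 + 1/10) gives -12.1 to +12.1 points. Newcombe gives -27.8 to +35.4. The exact unconditional score method gives about -30 to +40.
- The uncorrected width is zero with probability d(n1) x d(n2). Over the four SAP pairs that is 36-60%, 12-35%, 1-11% and 0.1-3% at rates of 5%, 10%, 20% and 30%.
- At assumed rates of 10% v 20%, in either direction, nominal 95% uncorrected limits cover 45-91% and Newcombe 95-99%.

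**5. Fisher's test on tables where the logit fails.** 1/3 v 0/17 gives p = 0.15, and 2/3 v 0/17 gives p = 0.016. For 10 v 10, 0 v 4 events gives p = 0.087, and 0 v 5 gives p = 0.033.

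**The case against.** **The comparison carries little weight.** Testing is informative only, the stopping rules in protocol 4.5 do not use it, and the overall and per-group percentages keep exact intervals. All of this stands and limits the severity. A reader might infer that the primary safety result itself is compromised; the documents do not support that.

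**The model still answers something.** A reader might infer that it yields no data-determined answer at all. That goes too far. The SAP's question is about percentages, and the fitted percentages, the direction of each contrast and the likelihood-ratio test do not depend on the intercept SD. What is undetermined is the size of the odds ratios and their Wald limits, which is what LSMEANS and the contrasts would report.

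**Software may return a variance of zero**, which reduces the model to an ordinary logit. That value would not be supported by the data, and step 2 of the working would still apply.

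**The protocol's Fisher test concerns two arms.** A reader might infer that 12.4.3 already prescribes an exact test for 3 v 7 v 10. It does not, because those groups exist only in the SAP. A three-group exact test is an extension of the protocol.

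**The interval point is conditional.** The limits collapse only if no continuity correction is applied, and SAP 7 does not mention one. Uncorrected limits are also not worse everywhere. For 3 v 17 at 5% in both groups they cover 98.7%, against 93.7% for Newcombe, largely because [0, 0] contains the true difference of zero.

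**TRTAN** is a label slip that should surface when the code is run. It is minor.

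**Conclusion.** The point holds as a low should-fix. The SAP departs without explanation from the protocol's named test on the sole primary endpoint. It also drops the 600V v 750V comparison to which that test applied. The replacement has an unidentified variance, so the reported odds ratios could lie anywhere from 0.33 to 0.06 in the worked example with no change in fit.

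The identification result follows from one binary record per patient and needs no assumed event rate; only the illustration uses assumed counts. The 44-98% chance of a group without a finite logit rests on assumed equal rates of 5% to 30%. The collapse of the difference limits is a related, secondary defect that depends on no continuity correction being used.

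**What to change.** **SAP 9.1**

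- Delete the random-intercept GLIMMIX step.
- Restore the protocol's 600V v 750V tabulation with Fisher's exact test. Label it as confounded: by SAP 3 every 600V patient had Generation 1 and every 750V patient Generation 2, and 3 of 10 v 0 of 10 had single treatment.
- Use Fisher's exact test for the SAP's own pairs: 3 v 7, 3 v 10, 7 v 10 and 3 v 17. Fisher-Freeman-Halton may be added as an overall test for Set 1, stated to be an extension of the protocol.
- If a model is preferred, drop the RANDOM statement, use exact or penalised logistic regression, correct LSMEANS, and document the departure from protocol 12.4.3.

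**SAP 7**

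- Replace the normal-approximation difference limits with an exact unconditional score interval, or with Newcombe and a note on its limitation at n = 3.
- Keep the exact overall and per-group intervals, and report every comparison as descriptive.

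**Cost.** SAP wording and short PROC FREQ code, with no new data. Difference intervals will be wider than the uncorrected limits when events are few. Fisher's test has very little power. At two-sided 0.05 and assumed rates of 10% v 30%, it is 0.3%, 0.2%, 7.6% and 0.2% for 3 v 7, 3 v 10, 7 v 10 and 3 v 17 with the larger group at 30%. With the smaller group at 30% it is 2.3%, 9.1%, 5.6% and 11.8%. Fisher-Freeman-Halton on Set 1 has 3-13%. The case for the change is validity and agreement with the protocol, not power.

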# 9.2. Analysis of the Secondary Effectiveness Endpoints

Endpoints have been classified relative to their distribution (binary, multinomial, or continuous), and the number of times the variable was recorded.

### **Binary Variable Assessed at a Single Time Point (3 endpoints):**

- **Secondary Endpoint:** Procedure success: defined as successful treatment of at least 6 cm of duodenum segment.
- **Secondary Endpoint:** Proportion of treated patients with an HbA1c improvement of  $\geq 0.5\%$  from baseline at 24 weeks (24 week score minus baseline score).
- **Secondary Endpoint:** Proportion of treated patients with an HbA1c improvement of >0.5% from baseline at 24 weeks maintained at 48 weeks.

For each set of results for each Comparison Set, the following 2 research questions will be addressed. Results will be presented using the Level 1 tables b through e.

For the endpoints measured on a binary scale, what are the overall estimates in the FAS population.

For the endpoints measured on a binary scale, is there a difference in the estimates in the FAS population based on the generation of the device, voltage, and single vs. double treatment?

#### Multinomial Variable Assessed at a Single Time Point (1 endpoint):

• **Secondary Endpoint:** Proportion of patients that have a change in glucose-lowering medication usage from baseline.

For each set of results for each Comparison Set, the following 2 research questions will be addressed. Results will be presented using the Level 1 tables b through e.

For this endpoint measured on a multinomial scale, what are the overall estimates in the FAS population.

For this endpoint measured on a multinomial scale, is there a difference in the estimates in the FAS population based on the generation of the device, voltage, and single vs. double treatment?

### **Continuous Variable Assessed at a Single Time Point (3 endpoints):**

- **Secondary Endpoint:** Procedure time: defined as the time between the Endogenex catheter insertion and the catheter removal.
- **Secondary Endpoint:** Change in liver enzyme from baseline at 24 weeks [Alanine Aminotransferase (ALT)].
- **Secondary Endpoint:** Change in liver enzyme from baseline at 24 weeks [Aspartate Aminotransferase (AST)].

For each set of results for each Comparison Set, the following 2 research questions will be addressed. Results will be presented using the Level 1 tables b through e.

For each endpoint measured on a continuous scale, what are the overall estimates in the FAS population.

For each endpoint measured on a continuous scale, is there a difference in the estimates in the FAS population based on the generation of the device, voltage, and single vs. double treatment?

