3 STUDY OBJECTIVES AND ENDPOINTS

The objective of this FIH study is to assess the feasibility and preliminary safety of the Endogenex Device for endoscopic duodenal mucosal regeneration in individuals with type 2 diabetes inadequately controlled on 2-3 non-insulin glucose-lowering medications.

The study will also assess, as exploratory endpoints, treatment efficacy, evaluated by changes in glycemic control and liver enzymes post procedure from baseline.

Objectives	Endpoints
Primary	
To assess the safety of the Endogenex Device for DMR procedure	Proportion of participants experiencing one or more device- or procedure-related serious adverse events at 12 weeks post procedure.
Secondary	
To assess the technical feasibility of the Endogenex Device for DMR procedure	 Procedure success: defined as successful treatment of at least 6 cm of duodenum segment. Procedure time: defined as the time between the Endogenex catheter insertion and the catheter removal.
To assess changes in glycemic control	 Change from baseline in glycemic parameters post index procedure, by visits
To assess changes in liver enzymes	 HbA1c Fasting plasma glucose (FPG) Insulin-resistance by HOMA-IR Post prandial plasma glucose (PPG), Beta cell function, disposition index by mixed meal tolerance test (MMTT) Time in range, glucose variability by continuous glucose monitoring (CGM) Proportion of treated participants with an HbA1c improvement of 0.5% or more at 24 weeks from
	 Proportion of treated participants with an HbA1c improvement of 0.5% or more at 24 weeks from baseline and maintained at 48 weeks Change in weight from baseline by visit Change in glucose-lowering medication usage Change in liver enzyme from baseline at 24 weeks Alanine Aminotransferase (ALT)

	o Aspartate Aminotransferase (AST)
•	Change from baseline in blood pressure and lipid profile by visit

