12 STATISTICAL DESIGN AND ANALYSIS

12.1 Statistical Overview

The primary endpoint, defined as the proportion of participants experiencing one or more device- or procedure-related serious adverse events, will be evaluated at week 12. Secondary endpoints will be assessed at times specified in Section 3, including presentation of change from baseline by visits for glycemic parameters, liver enzymes and other cardiometabolic metrices.

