12.4.4 Effectiveness Analysis

Secondary endpoints are summarized in Section 3. The primary analysis of the study's secondary endpoints will be performed using the mITT population. The analysis will also be performed using the PP population when appropriate.

Results for these endpoints will be tabulated and reported for each treatment arm at each timepoint for which data were specified to be collected, using change scores from baseline where appropriate. For binary outcomes, Fisher's exact test will be used to assess differences which may be present between groups, while t-tests or Wilcoxon's rank-sum will be applied for continuous outcomes depending on the normality assumption. Effectiveness endpoints collected at multiple timepoints post-intervention (e.g., HbA1c) will also be assessed longitudinally using repeated-measures mixed-effects models with time as the repeated measure and treatment arm as a factor variable. Assessment of overall change from baseline and comparisons between treatment arms will then be predicated principally upon these repeated-measures analyses.

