Serum Iron, ferritin, transferrin, saturation, serum folate, Vitamin D, Vitamin B12		Х									Х						X	Х	
CBC with differential	X	X		X		X		X			X			X			X	X	
Serum Glutamic acid decarboxylase antibody (Anti-GAD)	X																		
Thyroid-stimulating hormone (TSH)	X							$X^{[3]}$			$X^{[3]}$			$X^{[3]}$			$X^{[3]}$		
H. Pylori test	X	X																	
Pregnancy test [4]	X	X																	
International Normalized Ratio (INR) [7)		X																	
EKG		X																	
ENDOSCOPIES																			
DMR procedure			X																
Endoscopic follow up						X					X ^[5]								
SAFETY																			
Hypoglycaemic episodes	X	X	X	X	X	X	X	X	X	X	X	X	X	X	X	X	X	X	X
CGM		X	X	X	X	X	X	X	X	X	X	X	X	X	X	X	Х	X	X
Adverse events	X	X	X	X	X	X	X	X	X	X	X	X	X	X	X	X	X	X	X

^[1] Screening and baseline visits may be combined if screening visits or tests falls within baseline visit window.

^[2] Metabolic panel includes albumin, total protein, ALP, ALT, AST, bilirubin, BUN, creatinine, BUN/creatinine ratio, eGFR.

^[3] For participants on oral thyroid replacement therapy only.

^[4] For women with child-bearing potential.

^[5] Required if there were positive findings in the treated area at the 4-week endoscopy.

^[6] Only when MMTT is not performed.

^[7] INR is required prior to procedure only if participant is on Warfarin.

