Table 14.4.2 entitled Overall Summary of HbA1C, Fasting plasma glucose (FPG), Insulinresistance by HOMA-IR, and Post-prandial plasma glucose (PPG) by Visit (FAS Population)

Table 14.4.3 entitled Overall Summary of Beta Cell Function by Visit (FAS Population)

Table 14.4.4 entitled Overall Summary of HbA1c improvement  $\geq 0.3$  points by Visit (FAS Population)

Table 14.4.5 entitled Overall Summary of Percent Change in Body Weight by Visit (FAS Population)

Table 14.4.6 entitled Overall Summary of Glucose-Lowering Medications by Visit (FAS Population)

Table 14.4.7 entitled *Overall Summary of Liver Enzymes and Lipids by Visit (FAS Population)* 

Table 14.4.8 entitled Overall Summary of Blood Pressure Measurements by Visit (FAS Population)

Table 14.4.9 entitled Overall Summary of Continuous Glucose Monitoring (CGM) by Visit (FAS Population)

Version 1.0 Confidential Page 35 of 42

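### The SAP treats Week 24 ALT and AST changes as single-time-point variables although the enzymes are drawn at up to five follow-up visits, which fits poorly with its own sorting rule and the protocol's repeated-measures approach (minor)

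*SAP*

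**What the plan says.** SAP 9.2 opens with its sorting rule: "Endpoints have been classified relative to their distribution (binary, multinomial, or continuous), and the number of times the variable was recorded". It then lists three endpoints under "Continuous Variable Assessed at a Single Time Point (3 endpoints": procedure time, "Change in liver enzyme from baseline at 24 weeks [Alanine Aminotransferase (ALT" and the matching AST change. They go to the Level 1 tables, which SAP Section 7 reserves for results recorded once. No model is stated for the group comparison of these endpoints. SAP 7.3.1 bases every analysis on observed data and imputes only dates. The SAP also plans Table 14.4.7, "Overall Summary of Liver Enzymes and Lipids by Visit (FAS Population".

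In the protocol, Section 3 and the Protocol Summary define the endpoint at one week: "Change in liver enzyme from baseline at 24 weeks". Section 12.1 nevertheless announces "presentation of change from baseline by visits for glycemic parameters, liver enzymes and other cardiometabolic metrices". Section 12.4.4 says that effectiveness endpoints collected at several post-procedure visits "will also be assessed longitudinally using repeated-measures mixed-effects models with time as the repeated measure and treatment arm as a factor variable", and that overall change and arm comparisons rest chiefly on those models. It gives HbA1c as its example and does not name liver enzymes. In Appendix 2, footnote 2 reads "Metabolic panel includes albumin, total protein, ALP, ALT, AST, bilirubin, BUN, creatinine, BUN/creatinine ratio, eGFR".

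**The concern.** ALT and AST are recorded repeatedly, yet they are filed beside procedure time, which happens once. If the filing decides the analysis, the Week 24 result uses only patients with a Week 24 draw and ignores their Week 1, 12, 36 and 48 values. Liver-enzyme change is one of the SAP's three secondary objectives. If patients who miss Week 24 tend to be those who were doing less well earlier, the observed Week 24 mean is too favourable, and a repeated-measures model that uses the earlier values would remove most of that error. The groups are very small (3, 7 and 10 patients in SAP Section 3), so one missing draw can matter in a group comparison.

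**Working it through.** The documents give no sample-size figure, SD, visit correlation or expected number of missing draws for ALT or AST, so there is no planned figure to reproduce. The check counts the draws, sets the texts side by side, and sizes the consequence under stated assumptions.

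**1. Draws.** The metabolic-panel row of the Schedule of Activities is marked at screening, baseline, Weeks 1, 12, 24, 36 and 48, and the early discontinuation visit. That is 5 scheduled follow-up draws. The Protocol Summary lists liver enzymes at baseline and Weeks 12, 24 and 48, which is 3. On either count the variable is recorded more than once.

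**2. Texts side by side.**
- The SAP 9.2 rule sorts by how often the variable was recorded. By that rule ALT and AST are multiple-time-point variables.
- The SAP 9.2 list treats them as single-time-point. This matches the endpoint definition (Week 24) but not the stated rule.
- Table 14.4.7 shows liver enzymes by visit, which needs the repeated-measurement layout (Level 3), while SAP 9.2 sends them to Level 1.
- For HbA1c, FPG and HOMA-IR, SAP 4.2.1 names a mixed model for repeated measures with Week 24 as the principal time point. A Week 24 focus and a repeated-measures model are therefore compatible within this SAP.

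**3. Share of a group lost with one missing Week 24 draw.** 1/3 = 33%, 1/7 = 14%, 1/10 = 10%.

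**4. Precision if draws are missing at random.** Assume N = 20, m missing, and one other visit whose change correlates rho with the Week 24 change. Relative to no missing data:
- observed mean: SE ratio = sqrt(N/(N − m))
- repeated-measures estimate: SE ratio = sqrt(rho² + (1 − rho²)·N/(N − m))

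| m | Observed mean | Repeated measures, rho 0.3 | Repeated measures, rho 0.9 |
|---|---|---|---|
| 1 | 1.026 | 1.024 | 1.005 |
| 2 | 1.054 | 1.049 | 1.011 |
| 3 | 1.085 | 1.077 | 1.017 |
| 4 | 1.118 | 1.108 | 1.023 |

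The observed mean loses 3% to 12% in precision, and the model recovers part of that. Precision is not the main argument for the change.

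**5. Bias in an assumed worst case.** Suppose the m patients with the least favourable Week 12 change all miss Week 24. For normal change scores the bias of the observed Week 24 mean, in SDs of change, is rho × m/(N − m) × (mean of the m most extreme expected order statistics of 20). Those statistics are 1.867, 1.408, 1.131 and 0.921.
- m = 2: their mean is 1.638, and 2/18 × 1.638 = 0.182. Bias is 0.09 at rho 0.5 and 0.13 at rho 0.7.
- m = 4: their mean is 1.332, and 4/16 × 1.332 = 0.333. Bias is 0.17 at rho 0.5 and 0.23 at rho 0.7.

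The direction is toward benefit. An estimate that regresses Week 24 on Week 12 has bias near zero in the same setting, because missingness there depends only on an observed value. At an assumed SD of 15 U/L the worst-case bias is about 1.4 to 3.5 U/L (0.09 × 15 to 0.23 × 15).

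**6. Milder missingness.** If the odds of missing Week 24 only double per SD of worse Week 12 change, with 2 or 4 expected missing, the bias falls to about 0.03 to 0.09 SD. For scale, the SE of a 20-patient mean is 1/sqrt(20) = 0.22 SD.

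**7. No missing Week 24 value.** The overall Week 24 mean change is the same either way.

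**The case against.** The strongest defence is that the SAP sorts endpoints and not assays. The protocol defines liver enzymes at 24 weeks, while weight, blood pressure, lipids and the glycemic parameters are defined by visit, and the SAP repeats that split. It also files the Week 24 HbA1c responder endpoint as single-time-point, although HbA1c has five follow-up measurements. This stands as an explanation of the list, but it does not match the sorting rule that the SAP states.

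A reader might infer that the SAP breaches Protocol 12.4.4. The documents do not support that. The section does not name liver enzymes, and an endpoint fixed at one week can reasonably be read as outside it. Section 12.1 asks only that change be presented by visit, which Table 14.4.7 does.

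A reader might also infer that patients without a Week 24 draw vanish from the liver-enzyme results. They do not, because Table 14.4.7 still shows them at their other visits. The loss is confined to the Week 24 estimate and the group comparison.

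Lost draws are partly guarded against. Patients who meet rescue criteria early are asked to complete the Week 24 activities first, and the early discontinuation visit includes the metabolic panel. That reduces the problem but does not settle it: the SAP does not say that such an early draw counts as Week 24, and its expanded Week 24 window runs from day 152 to day 184.

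Finally, nothing in the documents links missed visits to liver enzymes, testing is declared informative only, and the study is unpowered. These points stand and keep the severity low.

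**Conclusion.** The point holds as a minor inconsistency. The single-time-point filing conflicts with the SAP's stated sorting rule and fits poorly with Protocol 12.1 and 12.4.4, but it follows the protocol's Week 24 definition of the endpoint.

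The size is conditional. With 2 to 4 of 20 Week 24 values missing in the assumed worst pattern and correlations of 0.5 to 0.7, the observed Week 24 mean is biased by about 0.1 to 0.2 SD toward benefit, at most about one standard error. It is smaller under milder missingness, and with no missing values the overall estimate is unchanged. The number missing, their pattern, the correlations and the 15 U/L SD are all assumptions. These figures concern the pooled mean and say nothing about the size of any bias in group contrasts. A reader might take them to show that the liver-enzyme result will be biased, but the documents give no basis for that. The repeated-measures estimate helps only patients with another post-procedure draw, and only if values are missing at random.

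**What to change.** Move ALT and AST to the multiple-time-point class in SAP 9.2. Analyse them with the mixed-model repeated-measures approach named for HbA1c, FPG and HOMA-IR in SAP 4.2.1, with Week 24 as the principal time point so that the endpoint is unchanged. State a simple covariance structure suited to 20 patients, since the SAP gives none for that model. Lipids are not a usable template, because the SAP names no model for them. Keep the observed Week 24 mean as a check and report the number missing at Week 24, overall and by group. This is consistent with SAP 7.3.1, because the model uses observed values without imputing any.

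If the sponsor prefers the Week 24 observed-data analysis, the minimum is to say so, explain why Protocol 12.4.4 is not applied to ALT and AST, correct the sorting rule, and report the number missing. Either way, reconcile the three-draw list in the Protocol Summary with the five draws in the Schedule of Activities.

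The cost is SAP wording, two further model runs and a covariance assumption. No new data or visits are needed.
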